## **6.8 Additional Considerations for Laboratory Procedures**

Each study site and laboratory involved in this study will comply with the DAIDS policy on Requirements for DAIDS Funded and/or Sponsored Laboratories in Clinical Trials Policy, which is available at:

<https://www.niaid.nih.gov/research/daids-clinical-research-policies-standard-procedures>

### **6.8.1 Specimen Collection**

Specimens will be collected for this study as indicated in the Schedule of Evaluations and per detailed guidance provided in the Laboratory Processing Chart (LPC), which will be available on the IMPAACT web site: [www.impaactnetwork.org](http://www.impaactnetwork.org).

In accordance with US National Institutes of Health (NIH) recommendations:

- Blood collection for pediatric participants (less than 18 years of age) will not exceed 5 mL/kg in a single day or 9.5 mL/kg in any eight-week period.
- Blood collection for adult participants (18 years of age and older) will not exceed 10.5 mL/kg or 550 mL, whichever is smaller, over any eight-week period.

In the event that the targeted blood collection volumes cannot be collected, available specimens should be prioritized for HIV-1 RNA first, followed by inflammatory biomarkers.

### **6.8.2 Specimen Preparation, Testing, Storage, and Shipping**

All specimens collected for this study will be labeled, transported, processed, tested, stored and/or shipped in accordance with the DAIDS policy referenced in Section 6.8, site and local laboratory SOPs, and the LPC. The frequency of specimen collection and testing will be directed by the Schedule of Evaluations and specifications for clinical management provided in [Section 8](#). The Laboratory Data Management System (LDMS) will be used to document specimen collection, testing, storage, and shipping as specified in LPC.

HIV-1 RNA (viral load) testing will be performed locally in a VQA-approved laboratory. Hair samples will be collected and stored locally and are expected to be batched shipped three times to designated testing laboratories for ARV concentration testing after all participant baseline, 6-month and 12-month at a site has been completed.

Plasma will be collected and stored locally until requested for shipment to designated testing laboratories. Testing (of plasma) for inflammatory biomarkers is expected to be performed after all participant follow-up has been completed. Inflammatory biomarkers will include hsCRP, d-dimer, IL1  $\beta$ , IL6, IL10, sCD14, and TNF $\alpha$ .

After all protocol-specified laboratory testing has been performed, residual specimens may be of interest for future research use. Participants (or their parents/guardians) will be asked to provide written informed consent for future research use of these specimens, if permitted by site IRBs/ECs and other applicable review bodies. Participants (or their parents/guardians) may choose to provide or to decline informed consent for future research use of residual specimens with no impact on other aspects of study participation.

### **6.8.3 Biohazard Containment**

As the transmission of HIV and other blood-borne pathogens can occur through contact with contaminated needles, blood, and blood products, appropriate blood and secretion precautions will be employed by all personnel in the drawing of blood and shipping and handling of all specimens for this study as currently recommended by the US Centers for Disease Control and Prevention, NIH, and other applicable agencies. All specimens will be shipped using packaging that meets requirements specified by the International Air Transport Association Dangerous Goods Regulations for UN 3373, Biological Substance, Category B, and Packing Instruction 650. Culture isolates, if obtained in this study, are to be shipped as specified for UN 2814 Category A Infectious Substances.

## **7 SAFETY ASSESSMENT, MONITORING, AND REPORTING**

Youth safety in the Pilot Test and Randomized Trial will be carefully assessed, monitored, and reported at multiple levels throughout this study. [Sections 7.1, 7.2, and 7.3](#) describe safety-related roles, responsibilities, and procedures. The safety monitoring roles of the Clinical Management Committee (CMC) and the IMPAACT Study Monitoring Committee (SMC) are briefly referenced in [Section 7.1](#) and described in greater detail in [Sections 9.4.1 and 9.4.2](#).

The specifications of this section apply to youth participants in both study arms. Refer to [Section 6.6](#) for additional information on potential social harms.

### **7.1 Safety-Related Roles and Responsibilities**

#### **7.1.1 Site Investigators**

Site investigators are responsible for continuous monitoring of youth participants in the Pilot Test and the Randomized Trial and for alerting the CMC if unexpected concerns arise.

Importantly, site investigators must inform the CMC of any of the following:

- Psychiatric adverse events resulting in hospitalizations
- Adverse events involving suicide attempts
- Any other occurrence that, in the opinion of the site investigator, could cause harm to a participant or others

For each of the above-listed types of events, the CMC should be informed as soon as possible and within three days of site awareness of the event.

Site investigators will enter safety-related data into electronic case report forms (eCRFs) as indicated in [Section 7.2](#) and complete expedited adverse event (EAE) reporting as indicated in [Section 7.3](#). Site investigators are also responsible for prompt reporting to their IRBs/ECs and other applicable review bodies of any unanticipated problems involving risks to participants or others.

### **7.1.2 Clinical Management Committee (CMC)**

The following Protocol Team members comprise the CMC: Co-Chairs, Medical Officers, Statisticians, Data Managers, Clinical Trial Specialists, and at least one Protocol Investigator. The CMC will provide guidance as needed to site investigators regarding all aspects of participant management, including but not limited to questions related to participant eligibility and management of adverse events, and study intervention administration. Refer to [Section 8](#) for more information on participant management.

On behalf of the full Protocol Team, the CMC will monitor participant safety through routine review of study data reports as described in [Section 9.4](#).

### **7.1.3 Study Monitoring Committee (SMC)**

An independent IMPAACT Study Monitoring Committee (SMC) will monitor participant safety through routine and as needed reviews of study data. Refer to [Section 9.4.2](#) for more information on the composition and role of the SMC in monitoring of this study.

## **7.2 Safety-Related Data Collection**

*Note: This section applies only to youth in the Pilot Test and Randomized Trial.*

*Note: This section describes eCRF data collection for pre-existing conditions and adverse events. As part of this description, reference is made to severity grading and criteria for EAE reporting; refer to [Sections 7.3.3](#) and [7.3.2](#), respectively, for detailed information on these topics.*

The definition of the term adverse event provided in Version 2.0 (January 2010) of the Manual for Expedited Reporting of Adverse Events to DAIDS (DAIDS EAE Manual) will be used in this study. This definition will be applied to youth participants, beginning at the time of enrollment/randomization in the Pilot Test or the Randomized Trial.

Pre-existing conditions and adverse events will be entered into eCRFs as specified below.

### ***Pre-Existing Conditions***

All psychiatric diagnoses identified prior to enrollment (including those ongoing at enrollment) will be entered into medical history eCRFs.

### ***Adverse Events***

The following adverse events will be entered into adverse event eCRFs.

- Grade 2 or higher suicidal ideation or attempt
- Grade 3 or higher psychiatric disorders
- Grade 3 or higher insomnia
- All adverse events meeting criteria for expedited adverse event reporting per [Section 7.3.2](#)

In addition, for any event that is assessed as serious as defined in Version 2.0 of the DAIDS EAE Manual due to the event resulting in hospitalization or prolongation of hospitalization, data regarding the hospitalization will be entered into eCRFs.

## **7.3 Expedited Adverse Event (EAE) Reporting**

*Note: This section applies only to youth participants in the Pilot Test and the Randomized Trial.*

### **7.3.1 EAE Reporting to DAIDS**

Requirements, definitions, and methods for expedited reporting of adverse events are outlined in Version 2.0 (January 2010) of the Manual for Expedited Reporting of Adverse Events to DAIDS (DAIDS EAE Manual), which is available on the DAIDS RSC website at: <https://rsc.niaid.nih.gov/clinical-research-sites/manual-expedited-reporting-adverse-events-daids>.

The DAIDS Adverse Experience Reporting System (DAERS), an internet-based reporting system, must be used for EAE reporting to DAIDS. In the event of system outages or technical difficulties, EAEs may be submitted using the DAIDS EAE Form. This form is available on the DAIDS RSC website at: <https://rsc.niaid.nih.gov/clinical-research-sites/paper-eae-reporting>.

For questions about DAERS, please contact NIAID CRMS Support at [[contact]](mailto:[contact]). Queries may also be sent from within the DAERS application itself.

For questions about expedited reporting, please contact the DAIDS RSC Safety Office at [[contact]](mailto:[contact]).

### **7.3.2 EAE Reporting Requirements for this Study**

The Serious Adverse Events (SAE) Reporting Category, as defined in Version 2.0 the DAIDS EAE Manual, will be used for this study. All serious (as defined in the DAIDS EAE Manual) psychiatric adverse events (e.g., insomnia, psychiatric disorders (including anxiety, depression, mania, and psychosis) and suicidal ideation or attempt) occurring among youth participants in the Pilot Test or the Randomized Trial will be reported as EAEs in this study.

The study interventions for which expedited reporting is required are the TI-CBT Intervention and the Discussion Control provided in the Pilot Test or Randomized Trial.

### 7.3.3 Grading Severity of Events (applies to EAEs and all other adverse events)

The Division of AIDS Table for Grading the Severity of Adult and Pediatric Adverse Events (DAIDS AE Grading Table), Corrected Version 2.1, dated July 2017, will be used in this study. This table is available on the RSC website at <https://rsc.niaid.nih.gov/clinical-research-sites/daids-adverse-event-grading-tables>.

### 7.3.4 EAE Reporting Period

The EAE reporting period for this study is the protocol-specified period of follow-up in the Pilot Test or Randomized Trial beginning at the time of enrollment/randomization and ending at the final follow-up visit.

After the protocol-defined EAE reporting period, unless otherwise noted, only Suspected, Unexpected Serious Adverse Reactions (SUSARs) as defined in Version 2.0 of the DAIDS EAE Manual will be reported to DAIDS if the study staff become aware of the events on a passive basis (from publicly available information).

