Step 8: Pilot Test	For the Pilot Test , IYL will deliver the complete TI-CBT intervention. Refer to Section 3.1.2 for more information on this step.

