Following completion of the Pilot Test at each site, study staff and local stakeholders will review the process information and feedback from the Pilot Test participants and discuss final adaptations of the TI-CBT Intervention for the site based on interest among youth and caregivers in participating; session length, attendance, and timing; and acceptability of intervention topics and activities. The core constructs of the intervention and the questionnaires planned to be used in the Randomized Trial will not be changed, but the Pilot Test outcomes may alter how the intervention is delivered or the timing or sequence of procedures performed in the Randomized Trial. A summary of Pilot Test findings and proposed changes will be documented at the site, with final approval to implement the changes provided by the protocol chairs and designated site staff. Agreed upon changes will be incorporated into the site’s TI-CBT Youth and Caregiver Intervention Manuals in preparation for the Randomized Trial.

Further detailed operational guidance on conducting and documenting Pilot Tests will be provided in the study-specific MOP.

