### 6.1.4 Youth Pilot Test: Group Sessions 1-6 Study Visits

Group Session 1 is targeted to occur on the day when group members complete their study Entry Visits. All six group sessions should be completed within eight weeks of the date of Group Session 1. Group sessions may be conducted on separate days or multiple sessions may be conducted on the same day.

Youth Group Sessions 1-6 Procedures for Pilot Test (within 8 weeks of Group Session 1)	
Behavioral and Counseling	

• IYL-delivered TI-CBT group session [refer to Section 5.1.1]

• Administer the following after the group session:

○ After each group session: Two questions on “Amount of fun had” and “Amount learned” [refer to Section 5.5.4]

○ After the final group session: Pen/paper-administered Participant Intervention Evaluation [refer to Section 5.5.4]

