### 9.4 Monitoring

The Randomized Trial will be monitored at multiple levels, consistent with standard IMPAACT procedures. A study monitoring plan that details monitoring roles and responsibilities and data to be reviewed at each level will be prepared before the study opens to accrual. The CMC ([Section 7.1.2](#)) is responsible for closely monitoring study progress, including timely achievement of key milestones, the quality of study conduct, and safety. IMPAACT leadership will also monitor study

progress and quality. The IMPAACT Study Monitoring Committee (SMC) will also conduct formal reviews of study conduct and safety. Unless otherwise specified, monitoring reports distributed to the protocol team will be pooled across the TI-CBT and Discussion Control Arms. Monitoring reports distributed to the SMC may be broken out by blinded study arm. In addition, an interim assessment of assumptions made in the power analysis will be performed as noted in [Sections 9.4.1 and 9.4.2](#).

[Section 7](#) provides more information on safety assessment and reporting. [Sections 10 and 11](#) provide more information on on-site monitoring and quality management at the site level. Further information on monitoring of study progress, quality of study conduct, and participant safety across sites is provided below.

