### **12.5.2 Unimproved Mental Health or Clinical Deterioration**

Continued or worsening of mental health symptoms is always a risk regardless of use of counseling. In addition, as suicidal ideation is a symptom of depression, suicide or suicide attempt is a risk. Clinical deterioration due to the underlying psychiatric condition(s), or the study intervention (TI-CBT), is also a risk.

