## APPENDICES

### Appendix I-A: Schedules of Evaluations for Youth – Pilot Test

Study Visit/Session	Screen	Pre-Entry 	Youth Group Sessions (within 8 weeks of session 1)					
			Entry/ Session 1 	Session 2	Session 3	Session 4	Session 5	Session 6/ Exit Visit
Clinical								
Informed Consent/Assent	X							
Review medical records (eligibility)/collect screen data	X							
Medical/medications history		X						
Youth decision on caregiver participation	X							
Mock hair sample (ART concentration)		X 						
Behavioral and Counseling								
TI-CBT Intervention			X	X	X	X	X	X
Administer questions on “fun had” and “learned”			X 	X 	X 	X 	X 	X 
Participant Intervention Evaluation Questionnaire								X 
Electronic questionnaires (pen and paper may be substituted per Section 10.1 )								
Patient Health Questionnaire – 9	X							
General Anxiety Disorder – 7	X							
UCLA PTSD-RI	X							
Demographics	X							
Disclosure		X 						
Self-reported ART adherence	X	X 						
Barriers to adherence		X 						
Gender-based Violence (WHO – Victim/Perpetrator)		X 						
Gender Roles (Rachel Jewkes)		X 						
AIDS-Related Stigma Scale		X 						
AIDS Risk Behavior Assessment		X 						
Children’s Report of Parenting Behavior Inventory		X 						
Laboratory								
HIV-1 test (confirmatory tests as needed)	5 mL							
Mock HIV-1 RNA (viral load) – no blood collected		X 						
Mock plasma for inflammatory biomarkers – no blood collected		X 						
Total Maximum blood volume	5 mL							

1. Pre-Entry Visit procedures should be conducted on the same day or up to 14 days prior to enrollment.
2. No data in the questionnaires are analyzed. Mock blood and hair collection: no specimens are collected.
3. Entry (enrollment) must occur within 60 days of screening and will be on the same day of Group Session 1. The day of Group Session 1 is considered Day 0 for youth.
4. Administer following completion of the group sessions.

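### Pilot Test youth have no scheduled symptom or psychiatric reassessment after entry, the end of their expedited reporting must be inferred, and the post-Pilot review lists no safety item

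*Protocol*

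**What the plan says.** **Who is exposed, and to what.** Pilot youth meet the same eligibility criteria as trial youth, including moderate to severe symptoms on at least one of three scales (Protocol 4.1.6, where suicidal ideation is not exclusionary). Table 1, Step 8 states that "IYL will deliver the complete TI-CBT intervention". Focus Groups deliver only selected components (3.1.1), so Pilot youth are the first at a site to receive the whole course. Section 4.6 bars a site from the Randomized Trial until it has piloted.

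**What is measured.** PHQ-9, GAD-7 and UCLA PTSD-RI are given at Screening only (6.1.1), and the targeted medical and psychiatric history is taken at Pre-Entry only (6.1.2). During Sessions 1–6 the listed procedures are the session, two questions on enjoyment and learning, and one paper evaluation of the intervention at the end (6.1.4). All six sessions should fall within eight weeks of Session 1. They can take less time: "Group sessions may be conducted on separate days or multiple sessions may be conducted on the same day".

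**When observation ends.** The last column of Appendix I-A is "Session 6/ Exit Visit". Section 7.3.4 has EAE reporting "beginning at the time of enrollment/randomization and ending at the final follow-up visit". After that, only SUSARs that staff learn of passively are reported.

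**What is reviewed before the trial opens.** Section 3.1.2 says that "study staff and local stakeholders will review the process information and feedback from the Pilot Test participants". The listed considerations are willingness to take part, session logistics, and acceptability of the content. The protocol chairs and designated site staff then approve a summary of findings and changes.

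**The concern.** The Pilot is the first use at each site of a locally adapted, peer-delivered course in distressed adolescents. Section 12.5.2 acknowledges that symptoms may worsen and that "suicide or suicide attempt is a risk". After entry, nothing on the schedule asks a Pilot youth about symptoms, new diagnoses, suicide attempts or mental health care. Detection depends on a youth raising the matter or on the site hearing of it some other way.

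A reporting period tied to a follow-up visit does not fit a component without one. The sensible reading is that it closes on the day of Session 6, but that has to be inferred, and a youth who stops attending has no defined end. Because the review before the Randomized Trial lists no safety item, even events that were collected need not reach the people who approve the next step.

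At stake is participant safety at the point where the plan could still adjust delivery at a site. The trial's efficacy estimate is not affected.

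**Working it through.** The plan states no sample size, event rate or precision target for Pilot safety (9.3.1 says none is warranted), so there is no figure to reproduce. The check compares the two schedules and then gives scale.

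**1. Scheduled symptom or history assessments after entry**
- Pilot (Appendix I-A): 0.
- Randomized Trial (Appendix II-A; 6.3.5, 6.3.6, 6.3.8): 3, at IPL, 6 months and 12 months.
- Table 7 has a follow-up block covering new psychiatric conditions and social harms; Table 6, for the Pilot, has none.

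**2. Length of the EAE window**
- Pilot: at most 8 × 7 = 56 days from Session 1 to Session 6, and less if sessions are combined.
- Randomized Trial: to Day 365 (allowable 335 to 395). Ratio 56/365 = 15%; range 56/395 = 14% to 56/335 = 17%.
- After the core sessions: 0 days in the Pilot, against 365 − 56 = 309 days in the Randomized Trial.
- The 309 days include the 6-month booster, which is further exposure. Measured from a booster on Day 182, follow-up is 365 − 182 = 183 days. From the latest allowed booster (Day 182 + 30 + 30 = 242) it is 365 − 242 = 123 days. That is about 4 to 6 months.

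**3. Age of the last symptom score.** Screening may be up to 60 days before enrollment, so by Session 6 the last score can be 60 + 56 = 116 days old.

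**4. Which detection routes operate after entry**
- The e-mail alert in 6.7 needs a response to a self-administered electronic question. None is scheduled in the Pilot after Pre-Entry.
- Youth leaders' notes (6.7) capture what is said in a session.
- Section 6.5 collects history according to the schedule, which for the Pilot means once, before exposure.
- Site monitoring, three-day notice to the Clinical Management Committee (CMC) for listed events, clinician response and follow-up to resolution (7.1.1, 8, 8.1) all apply once the site knows of an event.

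**5. Number of youth.** Eight sites (SAP 2.4) × 8 = 64, or 8 × 16 = 128 if every site needs two single-gender groups (9.3.1).

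**6. What a Pilot group could show.** The event rates p are assumptions; the documents give none. The chance of at least one event among n youth is 1 − (1 − p)^n.

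| p | n = 8 | n = 16 |
|---|---|---|
| 2% | 15% | 28% |
| 5% | 34% | 56% |
| 10% | 57% | 81% |

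If half the events arise or surface only after Session 6 (also an assumption), p is replaced by p/2. With 8 youth the chance of seeing one falls from 34% to 18% at p = 5%, and from 57% to 34% at p = 10%. With zero events seen, the one-sided 95% exact upper bound, 1 − 0.05^(1/n), is 31.2% for n = 8 and 17.1% for n = 16.

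**The case against.** The strongest reply is that Pilot safety is covered already. The opening of Section 7 names the Pilot and sends the reader to 9.4.1 and 9.4.2 for the CMC and Study Monitoring Committee (SMC) roles. Site investigators monitor continuously and notify the CMC within three days of suicide attempts and psychiatric hospitalizations. Youth leaders note suicidal talk, a supervisor is on site, staff who hear of concerns outside sessions have a defined route, and youth are contacted before each session (4.7). All of this stands. A reader might infer from the schedule that deterioration in the Pilot is neither looked for nor reported. The documents do not support that.

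Nor does adverse event reporting as a whole stop at Session 6. Section 7.3.4 limits expedited reporting only; 7.2 gives no end date for adverse events entered on case report forms, and Section 8 follows identified psychiatric events to resolution.

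A reader might also take the opening of 9.4, "The Randomized Trial will be monitored at multiple levels, consistent with standard IMPAACT procedures", to mean that the committees do not cover the Pilot. The cross-reference in Section 7 answers that. Still, 9.4 ties no safety review to the interval between a site's Pilot and its first randomization. The Pilot-specific trigger in 9.4.1 concerns acceptability and feasibility.

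It can also be said that the Pilot exists for adaptation and logistics, that eight uncontrolled youth are a weak basis for a safety decision, and that the manual of procedures, monitoring plan and site procedures, which are not among the documents, may fill the gap. The first two are true and limit what any fix can achieve. The third cannot be excluded, but the reporting end date belongs in the protocol.

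**Conclusion.** The point holds as an inexpensive safety improvement and a needed clarification. After entry the Pilot schedules no symptom or history assessment, against three in the Randomized Trial. Its EAE window is at most about 56 days, closes by inference at Session 6, and is undefined for a youth who misses that session. Worsening that is not volunteered is not actively sought, serious events arising after Session 6 fall outside the EAE period, and the post-Pilot review lists no safety item.

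Two further readings should be resisted.
- Because 12.5.2 names suicide attempt as a risk, a reader might conclude that one could never qualify as unexpected under the residual SUSAR rule. That turns on the DAIDS reporting manual, which is not among the documents.
- The 309 days of Randomized Trial reporting after the core sessions should not be called post-exposure follow-up. After the booster it is about 4 to 6 months.

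The conclusion assumes that the final follow-up visit means Session 6/Exit for the Pilot, and that no unseen procedure adds an assessment.

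**What to change.** 1. **Appendix I-A and 6.1.4:** add the PHQ-9 and the Section 6.5 questions at Session 6/Exit, by phone if the youth is absent. This detects worsening during the course, but not after it. If the PHQ-9 is given electronically, the alert in 6.7 can operate.
2. **Section 7.3.4:** state when the Pilot EAE period ends, including for a youth who misses Session 6, and extend it to 30 days after Session 6. The length is borrowed from the allowable IPL window in 6.3.5; it is not an existing reporting rule. An extended window alone remains passive, so add one brief Section 6.5 contact at 30 days if post-course events are to be actively sought.
3. **Section 3.1.2:** include Pilot adverse events in the summary that the protocol chairs and designated site staff approve before the site opens the Randomized Trial. A listing is enough. It need not become an outcome analysis, which 9.3.1 and SAP 2.1 exclude for the Pilot.

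**Cost.** One short questionnaire at an existing visit, one contact, and a tighter timeline. The Schema allows three months, about 91 days, for Pilot completion and review. If a group starts at the end of Pilot accrual, 56 + 30 = 86 days are used, leaving about 5 for review. Even with these changes, a Pilot of eight youth per site cannot rule out harm.
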